3.4.1.5 Surgery and Radiation

Use of radiotherapy or surgical intervention must be recorded on the appropriate Case Report Form. Localized radiation therapy to a site of pre-existing disease is permitted while on study.

Following approval by the medical monitor, the subject may continue with protocol therapy without interruption during the course of palliative radiation therapy if the investigator believes that the risk of excessive bone marrow suppression or other toxicity is acceptable, and it is in the best interest of the subject to do so.

If the subject develops a definite increase in the size of existing bone lesions or soft tissue plasmacytomas that meets the criteria for disease progression (see [Appendix 3](#)) treatment must be discontinued for progressive disease regardless of whether radiation therapy is initiated ([Section 3.5](#)).

3.4.2 Other Restrictions and Precautions

3.4.2.1 Treatment of Infusion Reactions

Infusion reactions should be graded according to CTCAE Version 4.0 allergic reaction/hypersensitivity. These reactions may manifest with signs and symptoms that may include, but are not limited to fever, chills, headache, rash, pruritus, arthralgias, hypo- or hypertension, bronchospasm or other symptoms. Severe infusion reactions require the immediate interruption of study drug therapy and permanent discontinuation from further treatment. Appropriate medical therapy including epinephrine, corticosteroids, intravenous antihistamines, bronchodilators, and oxygen should be available for use in the treatment of such reactions. Subjects should be carefully observed until the complete resolution of all signs and symptoms. Following an infusion reaction, subjects should be premedicated with acetaminophen and diphenhydramine for future treatments.

Nivolumab contains only human immunoglobulin protein sequences, and is therefore unlikely to be immunogenic and induce infusion or hypersensitivity reactions. However, if such a reaction were to occur, it might manifest with fever, chills, rigors, headache, rash, pruritus, arthralgias, hypo- or hypertension, bronchospasm, or other allergic-like reactions. All Grade 3 or 4 infusion reactions should be reported within 24 hours to the BMS Medical Monitor and reported as a SAE if criteria are met. Infusion reactions should be graded according to NCI CTCAE (version 4.0) guidelines.

Treatment recommendations are provided below and may be modified based on local treatment standards and guidelines, as appropriate.

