- Grade 3 (severe): Once reaction symptoms resolve, consider restarting the infusion at no more than half the rate at which the reaction occurred. If the subject does not experience additional symptoms, resume infusion rate escalation at increments and intervals as outlined in [Table 4.1.4.2-1](#). Repeat the procedure above in the event of recurrence of Grade 3 symptoms. Permanently discontinue daratumumab upon the third occurrence of a Grade 3 infusion-related reaction.
- Grade 4 (life threatening): Permanently discontinue daratumumab treatment.

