3.5.1 Additional Discontinuation Criteria - Nivolumab/Daratumumab Cohorts

In addition to the criteria defined above, subjects in the nivolumab/daratumumab cohorts (Cohort A and B) must discontinue study treatments for any of the following reasons:

- Confirmed progressive disease according to IMWG criteria ([Appendix 3](#)).
- Subjects who receive any non-protocol specified systemic anti-myeloma therapy before documented progression will be discontinued from all study treatment; however, tumor assessments will continue at 4-week intervals until documented progression.

- Subjects experiencing a Grade 4 infusion reaction related to daratumumab must discontinue daratumumab. Subjects may continue nivolumab with or without pomalidomide and dexamethasone treatment. Refer to [Section 4.1.5.2](#) for additional reasons to discontinue daratumumab dosing permanently.
- Subjects experiencing treatment related angioedema, Grade 4 rash, exfoliative or bullous rash, Stevens Johnson syndrome, or toxic epidermal necrolysis must discontinue pomalidomide and nivolumab. Subjects may continue on daratumumab and dexamethasone.
- Subjects experiencing \geq 8-week delay in all study drugs (nivolumab, daratumumab, pomalidomide, and dexamethasone) due to an AE(s) related to study treatment must be discontinued from all study treatment. Subjects experiencing delays unrelated to study therapy, for example due to radiation therapy, may delay study treatment up to 84 days. Further delays may be allowed after discussion with the BMS Medical Monitor.
- Subjects experiencing a Grade 4 or the third occurrence of a Grade 3 daratumumab infusion reaction must permanently discontinue daratumumab
- Subjects experiencing a Grade 3 or 4 infusion reaction related to nivolumab must discontinue nivolumab. Subjects may continue daratumumab with or without pomalidomide and dexamethasone treatment. Refer to [Section 4.1.5.1](#) for additional reasons to discontinue nivolumab dosing permanently.

Continuation of study treatments in the circumstance of one or more study treatments being discontinued or delayed should follow these criteria:

- Subjects who experience AEs that require discontinuation of daratumumab may be allowed to continue therapy with nivolumab, with or without pomalidomide and dexamethasone, if deemed in their best interest by both the PI and the BMS medical monitor. Subjects must be deriving clinical benefit.

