4 TREATMENTS

Study drugs include both Noninvestigational (NIMP) and Investigational Medicinal Products (IMP) and can consist of the following:

- All products, active or placebo, being tested or used as a comparator in a clinical trial
- Study required premedication, and
- Other drugs administered as part of the study that are critical to claims of efficacy (eg, backbone therapy, rescue medications)

Investigational Product

An investigational product, also known as investigational medicinal product in some regions, is defined as a pharmaceutical form of an active substance or placebo being tested or used as a reference in a clinical study, including products already with a marketing authorization but used or assembled (formulated or packaged) differently than the authorized form, or used for an unauthorized indication, or when used to gain further information about the authorized form.

The investigational product should be stored in a secure area according to local regulations. It is the responsibility of the investigator to ensure that investigational product is only dispensed to study subjects. The investigational product must be dispensed only from official study sites by authorized personnel according to local regulations.

In this protocol, investigational product(s) is/are: nivolumab and daratumumab.

Noninvestigational Product

Other medications used as support or escape medication for preventative, diagnostic, or therapeutic reasons, as components of the standard of care for a given diagnosis, may be considered as noninvestigational products.

Handling and Dispensing

The product storage manager should ensure that the study drug is stored in accordance with the environmental conditions (temperature, light, and humidity) as determined by the sponsor. If concerns regarding the quality or appearance of the study drug arise, do not dispense the study drug and contact the sponsor immediately.

Investigational product documentation must be maintained that includes all processes required to ensure drug is accurately administered. This includes documentation of drug storage, administration and, as applicable, storage temperatures, reconstitution, and use of required processes (eg, required diluents, administration sets).

For nivolumab and daratumumab, please refer to the current IB/pharmacy reference sheets for storage, handling and preparation instructions.

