4.1 Study Treatments - Nivolumab/Daratumumab Cohorts

For product descriptions see [Table 4.1-1](#). Non-investigational medicinal product will be used to treat infusion reactions as described in [Section 3.4.2.1](#).

Table 4.1-1: Product Description - Nivolumab/Daratumumab Cohorts, Treatment Period

Product Description and Dosage Form	Potency	IP/ Non IP	Primary Packaging (Volume)/ Label Type	Secondary Packaging (Qty) /Label Type	Appearance	Storage Conditions (per label)
BMS-936558-01 (nivolumab) Solution for injection	100 mg (10 mg/mL)	IP	10 mL vial/ Open-Label	5 or 10 vials per carton/ Open-Label	Clear to opalescent, colorless to pale yellow liquid. May contain particles.	2 - 8°C Protect from light and freezing.
Pomalidomide Capsules*	1 mg, 2 mg, 3 mg, and 4 mg	Non IP	Market Product Configuration	Market Product Configuration	As per US commercial product.	As per Package Insert
Daratumumab Injection for Intravenous Infusion	100 mg (20 mg/mL) and/or 400 mg (20 mg/mL)	IP	Vial	Carton	Colorless to pale yellow solution in a vial.	As per Package Insert/ clinical supply label
Dexamethasone Solution**	4 mg/mL, 8 mg/mg, or other strengths	Non IP	Various Packaging Configurations	Various Packaging Configurations	Various	As per Package Insert
Dexamethasone tablets**	2 mg, 4 mg, or other strengths	Non IP	Various Packaging Configurations	Various Packaging Configurations	Various	As per Package Insert

IP= investigational product

*Pomalidomide should be obtained by the investigator sites standard prescribing procedures where allowed.

**Dexamethasone solution and tablets will be procured by the investigative sites.

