Administration of daratumumab may be restarted upon recovery from toxicity to Grade 2 or baseline, with the exception that Grade 2 laryngeal edema or Grade 2 bronchospasm must be fully recovered.

Any adverse event deemed to be related to daratumumab that requires a dose hold of more than 4 weeks (Cycle 1 to Cycle 6) or more than 6 weeks (Cycle 7 and beyond) will result in permanent discontinuation of daratumumab.

In order to initiate a new infusion of daratumumab the following criteria must be met:

- Platelet count $\geq 50 \times 10^9/L$ (platelet transfusion support is allowed)
- ANC $\geq 0.50 \times 10^9/L$ (growth factor support is strongly recommended if ANC $< 1.0 \times 10^9/L$).

For subjects who have experienced HBV reactivation while on study treatment, if the benefits outweigh the risks, study treatment may be resumed with concomitant antiviral prophylaxis as per local standard of care.

Daratumumab Dose Discontinuation Due to Adverse Events

Daratumumab treatment should be permanently discontinued for the following reasons:

- Grade 4 infusion reaction related to daratumumab.
- The 3rd occurrence of a Grade 3 daratumumab infusion related reaction
- Subjects experiencing ≥ 8 -week delay in all study drugs (nivolumab, daratumumab, pomalidomide, and dexamethasone) due to an AE(s) related to study treatment must be discontinued from all study treatment. Subjects experiencing delays unrelated to study therapy, for example due to radiation therapy, may delay study treatment up to 84 days. Further delays may be allowed after discussion with the BMS Medical Monitor.
- Any daratumumab related AE that requires a dose hold of > 4 weeks (Cycle 1 to Cycle 6) or > 6 weeks (Cycle 7 and beyond) will result in permanent discontinuation of daratumumab, unless, upon consultation with the sponsor and the review of safety and efficacy, continuation is agreed upon.

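### Protocol 3.4.2.1 orders a permanent stop after a severe infusion reaction without naming a drug, which conflicts with the daratumumab rules for a first or second Grade 3 reaction

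*Protocol*

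**What the plan says.** Protocol 3.4.2.1, under a general heading on treating infusion reactions, states: "Severe infusion reactions require the immediate interruption of study drug therapy and permanent discontinuation from further treatment". It gives no grade number, names no drug and makes no exception.

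Protocol 3.4.1.4, on daratumumab reactions, states: "Grade 3 (severe): Once reaction symptoms resolve, consider restarting the infusion at no more than half the rate at which the reaction occurred". It has the same procedure repeated if Grade 3 symptoms recur, and then: "Permanently discontinue daratumumab upon the third occurrence of a Grade 3 infusion-related reaction". Grade 4 is a permanent stop.

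Two further sections give the same thresholds. Protocol 3.5.1: "Subjects experiencing a Grade 4 or the third occurrence of a Grade 3 daratumumab infusion reaction must permanently discontinue daratumumab". Protocol 4.1.5.2 lists among its reasons for permanent daratumumab discontinuation: "The 3rd occurrence of a Grade 3 daratumumab infusion related reaction".

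For nivolumab, Protocol 3.5.1 states: "Subjects experiencing a Grade 3 or 4 infusion reaction related to nivolumab must discontinue nivolumab". Section 3.4.2.2 agrees.

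On what counts as study drug, Protocol 4 states: "In this protocol, investigational product(s) is/are: nivolumab and daratumumab". The same section counts products under test as study drugs.

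**The concern.** A stopping instruction is mandatory, so two sites reading the same protocol should reach the same action. Here a site that applies 3.4.2.1 as written would end daratumumab for good at the first Grade 3 reaction. A site that applies 3.4.1.4 could restart and continue until a third.

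The D arm of Cohort B is where this bites most directly. Daratumumab is its only study drug, so the choice of section decides whether the subject stays on any study treatment. In the ND arm, Protocol 3.1 allows nivolumab to continue after daratumumab is stopped, if the investigator and medical monitor agree and the subject is benefiting.

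Two things follow for the analysis. Daratumumab exposure would depend partly on how the site reads the protocol. The window for the primary safety endpoints, which closes 100 days after the last dose (Protocol 8.3.1.1, SAP 4.1), would close earlier for a subject stopped early.

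**Working it through.** No formula applies; the check is a comparison of rules. As to daratumumab, the sections read as follows.

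| Daratumumab reaction | 3.4.2.1, read literally | 3.4.1.4 | 3.5.1 and 4.1.5.2 |
|---|---|---|---|
| First Grade 3 | permanent stop | restart may be considered | stopping threshold not reached |
| Second Grade 3 | permanent stop | procedure repeated | stopping threshold not reached |
| Third Grade 3 | permanent stop | permanent stop | permanent stop |
| Grade 4 | permanent stop | permanent stop | permanent stop |

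The conflict is confined to the first two rows. It rests on three steps.

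1. *Does the sentence in 3.4.2.1 reach daratumumab?* As worded, yes. It speaks of study drug therapy, and Protocol 4 makes daratumumab an investigational product and hence a study drug. Section 4.1.1.2 also says that daratumumab can cause severe infusion reactions, whereas 3.4.2.1 calls such reactions unlikely with nivolumab.
2. *Does severe include Grade 3?* Section 3.4.1.4 attaches that word to Grade 3 for daratumumab. Section 3.4.2.2 attaches it to Grades 3 and 4 for nivolumab.
3. *Does anything say which section prevails?* No sentence gives the daratumumab section precedence. The allowance in 3.4.2.1 for local modification covers the treatment recommendations that come after it, not the stopping sentence before it.

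For nivolumab the same comparison shows no conflict: 3.4.2.1, 3.4.2.2 and 3.5.1 all stop nivolumab at Grade 3 or 4.

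On origin, the same sentence stands in 3.4.2.1 of the older protocol appended to the document (revised 01-Oct-2015), whose investigational products were nivolumab, ipilimumab and lirilumab. In the current text, neighbouring wording has been narrowed to nivolumab, while this sentence still refers to study drug. That it is left over from the older text is an inference.

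On scale, Cohort B plans about 60 subjects at 2:1, that is 40 ND and 20 D. One D subject is 1/20 = 5% of that arm and one ND subject is 1/40 = 2.5%. The documents give no Grade 3 daratumumab reaction rate. Section 4.1.1.2 says only that about half of patients had a reaction, without grade.

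**The case against.** The strongest reply is that 3.4.2.1 is plainly about nivolumab. Its second paragraph discusses only nivolumab, and the recommendations it points to are the nivolumab guidelines in 3.4.2.2. The nivolumab dosing section, 4.1.4.1, sends acute reactions to it. Its advice to premedicate after a reaction adds little for daratumumab, where an antihistamine and paracetamol are already given before every infusion. Daratumumab has its own titled section, and its threshold appears three times without variation, twice in the formal discontinuation criteria. A reader who prefers the specific rule to the general one would follow those.

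Much of this stands. The nivolumab reading is plausible, and many sites may already adopt it. But it has to be inferred against an unqualified mandatory sentence.

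Three stronger readings are tempting, and the documents do not support them.

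- *That Section 4.1 extends the stopping rule to daratumumab.* It says "Non-investigational medicinal product will be used to treat infusion reactions as described in" Section 3.4.2.1. That concerns supportive medication, not discontinuation.
- *That 3.5.1 authorises restart.* It sets a threshold and does not mention restart. Restart is described in 3.4.1.4.
- *That PFS or ORR follow-up is lost.* Protocol 3.6 and 5.4.1.2 require assessments to continue until progression after treatment stops, even if new therapy begins. What remains is indirect: the SAP's primary PFS definition (4.2.2) censors at subsequent therapy, so an earlier stop could alter PFS if it led to earlier new therapy.

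**Conclusion.** The point holds as an internal inconsistency in a safety instruction. For a first or second Grade 3 daratumumab reaction, 3.4.2.1 as written requires a permanent stop and 3.4.1.4, 3.5.1 and 4.1.5.2 do not. At Grade 4, and at a third Grade 3, all four agree on daratumumab.

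The consequence is inconsistent daratumumab exposure and an adverse event window that closes at a different time, most directly in the D arm. No number of affected subjects can be given from the documents. A reader might multiply an assumed Grade 3 rate by the arm sizes, but that product would also assume that sites follow 3.4.2.1 over three concordant daratumumab rules. If every site follows the daratumumab rules, nobody is handled differently. The case for correction rests on the contradiction and the small cost of removing it, not on a projected count.

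**What to change.** State in Protocol 3.4.2.1 which drug or drugs its discontinuation sentence governs, and reconcile it with 3.4.1.4, 3.5.1 and 4.1.5.2. Those four sections should then give the same action for the same drug, grade and occurrence. The clinical team must decide the rule; none is proposed here.

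The cost is about one sentence. If it only clarifies scope, an administrative letter may suffice; the Document History shows such letters already used to correct eligibility criteria and a daratumumab resumption criterion. If the team changes a threshold, a protocol revision under 9.1.1 is needed. The SAP needs no change: its dose-change listing (7.4.2) already carries the reason for discontinuation, so any subject stopped at a first or second Grade 3 daratumumab reaction can be looked for there.

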3.4.2.2 Guidelines for Nivolumab-related Infusion Reactions

For Grade 1 symptoms: (Mild reaction; infusion interruption not indicated; intervention not indicated)

Remain at bedside and monitor subject until recovery from symptoms. The following prophylactic premedications are recommended for future infusions: diphenhydramine 50 mg (or equivalent) and/or acetaminophen/paracetamol 325 to 1000 mg at least 30 minutes before additional nivolumab administrations.

For Grade 2 symptoms: (Moderate reaction requires therapy or infusion interruption but responds promptly to symptomatic treatment [eg, antihistamines, non-steroidal anti-inflammatory drugs, narcotics, corticosteroids, bronchodilators, IV fluids]; prophylactic medications indicated for ≤ 24 hours):

- Stop the nivolumab infusion, begin an IV infusion of normal saline, and treat the subject with diphenhydramine 50 mg IV (or equivalent) and/or acetaminophen/paracetamol 325 to 1000 mg; remain at bedside and monitor subject until resolution of symptoms. Corticosteroid and/or bronchodilator therapy may also be administered as appropriate. If the infusion is interrupted, then restart the infusion at 50% of the original infusion rate when symptoms resolve; if no further complications ensue after 30 minutes, the rate may be increased to 100% of the original infusion rate. Monitor subject closely. If symptoms recur then no further nivolumab will be administered at that visit.
- For future infusions, the following prophylactic premedications are recommended: diphenhydramine 50 mg (or equivalent) and/or acetaminophen/paracetamol 325 to 1000 mg should be administered at least 30 minutes before nivolumab infusions. If necessary, corticosteroids (up to 25 mg of hydrocortisone or equivalent) may be used.

For Grade 3 or Grade 4 symptoms: (Severe reaction, Grade 3: prolonged [ie, not rapidly responsive to symptomatic medication and/or brief interruption of infusion]; recurrence of symptoms following initial improvement; hospitalization indicated for other clinical sequelae [eg, renal impairment, pulmonary infiltrates]. Grade 4: life-threatening; pressor or ventilatory support indicated):

- Immediately discontinue infusion of nivolumab. Begin an IV infusion of normal saline and treat the subject as follows: Recommend bronchodilators, epinephrine 0.2 to 1 mg of a 1:1000 solution for subcutaneous administration or 0.1 to 0.25 mg of a 1:10,000 solution injected slowly for IV administration, and/or diphenhydramine 50 mg IV with methylprednisolone 100 mg IV (or equivalent), as needed. Subject should be monitored until the investigator is comfortable that the symptoms will not recur. **Nivolumab will be permanently discontinued.** Investigators should follow their institutional guidelines for the treatment of anaphylaxis. Remain at bedside and monitor subject until recovery from symptoms.

In the case of late-occurring hypersensitivity symptoms (e.g., appearance of a localized or generalized pruritus within 1 week after treatment), symptomatic treatment may be given (eg, oral antihistamine or corticosteroids).

3.5 Discontinuation of Subjects from Treatment

Subjects MUST discontinue investigational product (and noninvestigational product at the discretion of the investigator) for any of the following reasons:

- Withdrawal of informed consent (subject's decision to withdraw for any reason)
- Any clinical AE, abnormal laboratory test results or intercurrent illness which, in the opinion of the investigator, indicates that continued participation in the study is not in the best interest of the subject
- Grade 3 or 4 uveitis related to nivolumab
- Pregnancy
- Termination of the study by BMS
- Loss of ability to freely provide consent through imprisonment or involuntary incarceration for treatment of either a psychiatric or physical (e.g., infectious disease) illness
- Documented and confirmed disease progression or clinical deterioration while receiving active study therapy
- Stopping rules as defined in [Section 3.1.1.1](#).
- Severe nivolumab immune-mediated adverse events, as described in [Appendix 5](#).

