Subjects may resume treatment with nivolumab when the drug-related AE(s) resolve(s) to Grade ≤ 1 or baseline, with the following exceptions:

- Subjects may resume treatment in the presence of Grade 2 fatigue
- Subjects who have not experienced a Grade 3 drug-related skin AE may resume treatment in the presence of Grade 2 skin toxicity
- Subjects with baseline Grade 1 AST/ALT or total bilirubin who require dose delays/interruptions for reasons other than a 2-grade shift in AST/ALT or total bilirubin may resume treatment in the presence of Grade 2 AST/ALT OR total bilirubin
- Subjects with combined Grade 2 AST/ALT AND total bilirubin values meeting discontinuation parameters should have treatment permanently discontinued
- Drug-related pulmonary toxicity, diarrhea, colitis, uveitis or neurologic toxicity must have resolved to baseline before treatment is resumed. Subjects with persistent Grade 1 pneumonitis after completion of a steroid taper over at least 1 month may be eligible for retreatment if discussed with and approved by the BMS Medical Monitor.
- Drug-related endocrinopathies adequately controlled with only physiologic hormone replacement may resume treatment after consultation with the BMS Medical Monitor.

Dose delay/interruption of nivolumab which results in treatment interruption of > 8 weeks require treatment discontinuation, with exceptions as noted below.

Nivolumab Dose Discontinuation Due to Adverse Events

Nivolumab treatment should be permanently discontinued for the following reasons:

- Any Grade 2 drug-related uveitis, eye pain or blurred vision that does not respond to topical therapy and does not improve to Grade 1 severity within the re-treatment period OR requires systemic treatment

- Any Grade 3 non-skin, drug-related AE lasting > 7 days, with the following exceptions for laboratory abnormalities, drug-related uveitis, pneumonitis, bronchospasm, hypersensitivity reactions, infusion reactions, and endocrinopathies:
 - Grade 3 drug-related uveitis, pneumonitis, bronchospasm, neurologic toxicity, myocarditis, hypersensitivity reaction, or infusion reaction of any duration requires discontinuation
 - Grade 3 drug-related endocrinopathies adequately controlled with only physiologic hormone replacement do not require discontinuation. Adrenal insufficiency requires discontinuation regardless of control with hormone replacement
 - Grade 3 drug-related laboratory abnormalities do not require treatment discontinuation except:

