 - ◆ Grade 3 drug-related thrombocytopenia > 7 days or associated with bleeding requires discontinuation
 - ◆ Grade ≥ 3 drug-related AST, ALT or Total Bilirubin requires discontinuation*
 - ◆ Concurrent AST or ALT > 3 x ULN and total bilirubin > 2x ULN
- * In most cases of Grade 3 AST or ALT elevation, study treatment will be permanently discontinued. If the investigator determines a possible favorable benefit/risk ratio that warrants continuation of study treatment, a discussion between the investigator and the BMS Medical Monitor/designee must occur.
- Any Grade 4 drug-related adverse event or laboratory abnormality (including but not limited to creatinine, AST, ALT, or Total Bilirubin), except for the following events which do not require discontinuation:
 - Grade 4 neutropenia ≤ 7 days
 - Grade 4 lymphopenia or leukopenia or asymptomatic amylase or lipase
 - Isolated Grade 4 electrolyte imbalances/abnormalities that are not associated with clinical sequelae and are corrected with supplementation/appropriate management within 72 hours of their onset
 - Grade 4 drug-related endocrinopathy adverse events, such as, hyper- or hypothyroidism, or glucose intolerance, which resolve or are adequately controlled with physiologic hormone replacement (corticosteroids, thyroid hormones) or glucose-controlling agents, respectively, may not require discontinuation after discussion with and approval from the BMS Medical Monitor.
 - Any event that leads to delay in dosing lasting > 8 weeks from the previous dose requires discontinuation, with the following exceptions:
 - Dosing delays to allow for prolonged steroid tapers to manage drug-related AEs are allowed. Prior to re-initiating treatment in a subject with a dosing delay lasting > 8 weeks from the previous dose, the BMS medical monitor must be consulted. Tumor assessments should continue as per protocol even if dosing is delayed/interrupted. Periodic study visits to assess safety and laboratory studies should also continue as clinically indicated during such dosing delays/interruption.
 - Dosing delays lasting > 8 weeks from the previous dose that occur for non-drug-related reasons may be allowed if approved by the BMS medical monitor. Prior to re-initiating

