4.1.5.2 Daratumumab

In Cycles 1 to 2, daratumumab doses that fall outside of the pre-specified window of +3 days must be skipped.

In Cycle 3 through 6, daratumumab dosing may be delayed for up to 1 week. If unable to administer within 1 week, then the dose should be skipped and resumption of the daratumumab continues per the protocol defined schedule.

From Cycle 7 and beyond, daratumumab can be delayed within a 21-day window. Doses that fall outside the allowed window should be skipped.

Subjects experiencing a Grade 4 (life threatening) infusion reaction related to daratumumab must permanently discontinue daratumumab.

Daratumumab Dose Delays Due to AEs

On the first day of each new treatment cycle and before each daratumumab dose, the subject will be evaluated for possible toxicities that may have occurred after the previous dose(s). Dose modifications or delays will be made based on the toxicity experienced during the previous cycle of therapy or newly encountered on Day 1 of a cycle.

Daratumumab administration should be delayed if any of the following criteria below are met, to allow for recovery from toxicity related to the study drug:

- Grade 4 hematologic toxicity except for grade 4 lymphopenia
- Grade \geq 3 thrombocytopenia
- Febrile neutropenia
- Neutropenia with infection, of any grade
- Grade \geq 3 non-hematologic toxicities with the following exceptions:
 - Grade 3 nausea or Grade 3 vomiting that responds to antiemetic treatment within 7 days
 - Grade 3 diarrhea that responds to antidiarrheal treatment within 7 days
 - Grade 3 fatigue or asthenia that was present at baseline or that lasts for < 7 days after the last administration of daratumumab

If daratumumab administration does not commence within the prespecified windows of the scheduled administration date (Table 4.1.5.2-1), that respective dose should be skipped. Administration may resume at the next planned dosing date. A missed dose will not be made up.

Table 4.1.5.2-1: Daratumumab Windows of Dosing Resumption

Cycles	Dosing Frequency	Skip dose window	Dosing Resumption
1 and 2	Weekly (QW)	> 3 days	Next planned weekly dosing date
3 to 6	Biweekly (Q2W)	> 7 days	Next planned biweekly dosing date
7 and beyond	Every 4 weeks (Q4W)	> 21 days	Next planned every 4 weeks dosing date

Criteria to Resume Treatment with Daratumumab

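### Section 3.5, read with the Section 4 definition, stops daratumumab as well as nivolumab for Grade 3-4 nivolumab-related uveitis, although Sections 3.1, 3.5.1 and 4.1.5 allow daratumumab to continue

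*Protocol*

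**What the plan says.** Protocol Section 3.5 sets out the reasons for which treatment has to end. Its lead-in is "Subjects MUST discontinue investigational product (and noninvestigational product at the discretion of the investigator) for any of the following reasons", and one of the reasons is "Grade 3 or 4 uveitis related to nivolumab". Discretion is given only for noninvestigational product. Section 4 supplies the definition: "In this protocol, investigational product(s) is/are: nivolumab and daratumumab".

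The drug-specific sections deal with the same event separately.

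- Section 4.1.5.1 introduces its list with "Nivolumab treatment should be permanently discontinued for the following reasons". The list includes "Grade 3 drug-related uveitis, pneumonitis, bronchospasm, neurologic toxicity, myocarditis, hypersensitivity reaction, or infusion reaction of any duration requires discontinuation" and "Any Grade 4 drug-related adverse event or laboratory abnormality". Uveitis is not among the Grade 4 exceptions. The section concerns nivolumab and gives no instruction on daratumumab.
- Section 4.1.5.2 states "Daratumumab administration should be delayed if any of the following criteria below are met, to allow for recovery from toxicity". The sentence goes on to limit this to toxicity related to 'the study drug'. Grade 3 or higher non-hematologic toxicity is one of the criteria. The exceptions are certain nausea, vomiting, diarrhea, fatigue and asthenia. Its separate list of reasons for ending daratumumab permanently does not mention uveitis.
- Sections 3.1, 3.5.1 and 4.1.5 each allow the remaining drug or drugs to continue when one is stopped. The conditions are that the investigator and the sponsor's medical monitor agree and that the subject is deriving clinical benefit.

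**The concern.** A subject in a nivolumab-daratumumab arm who develops this event falls under two instructions that differ for daratumumab. A site that follows 3.5 to the letter withdraws daratumumab, an active anti-myeloma drug, from a relapsed or refractory patient whom three other sections would allow to stay on it. A site that uses the continuation permission departs from a compulsory rule, and Section 9.1.1 does not allow deviations without prior ethics approval except to remove an immediate hazard. Different sites could therefore handle the same event differently, and the reason recorded for ending daratumumab would depend on which section was consulted.

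**Working it through.** The conflict itself involves no arithmetic. The rules are set side by side for one case: Grade 3 or 4 uveitis attributed to nivolumab.

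| Protocol section | Nivolumab | Daratumumab |
|---|---|---|
| 3.5 with the Section 4 definition | Stop | Stop |
| 4.1.5.1 | Stop permanently | Not addressed |
| 4.1.5.2, permanent stops | Not addressed | Uveitis not listed |
| 4.1.5.2, delays | Not addressed | Delay, if 'the study drug' includes nivolumab |
| 3.1, 3.5.1, 4.1.5 | Already stopped | May continue, with agreement and clinical benefit |

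1. Taken alone, 4.1.5.1 is compatible with 3.5, because it says nothing about daratumumab. What it does is make the event one that ends nivolumab, and that is the condition under which 3.1, 3.5.1 and 4.1.5 permit daratumumab to continue.
2. The first and last rows then disagree: 3.5 compels a stop where the last row permits continuation.
3. Section 3.5.1 does not settle it. Its compulsory criteria are stated to apply in addition to those of 3.5. Its continuation block has its own lead-in, but it neither says that it prevails over 3.5 nor exempts uveitis.
4. Elsewhere the protocol names the drug to be stopped. In 3.5.1 a Grade 3-4 nivolumab infusion reaction ends nivolumab and daratumumab may continue; Stevens Johnson syndrome ends pomalidomide and nivolumab, and daratumumab may continue. The uveitis bullet names nivolumab as the cause but not as the drug to stop.

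For size, the documents give no uveitis rate, so the range below is an assumption.

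- Cohort B combination arm: 60 × 2/3 = 40 subjects (Synopsis, Sample Size).
- At 0.5%: 40 × 0.005 = 0.2 expected cases; chance of at least one, 1 − 0.995^40 = 18%.
- At 5%: 40 × 0.05 = 2 expected cases; chance of at least one, 1 − 0.95^40 = 87%.

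Daratumumab doses at stake for an affected Cohort B subject (Sections 4.1.4.1 and 4.1.4.2, counting a split first dose as one): Cycles 1-2 have 4 × 2 = 8 and Cycles 3-6 have 2 × 4 = 8, a total of 16.

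- Event after the first nivolumab dose (Cycle 1 Day 15): 3 given, 16 − 3 = 13 forgone.
- After Cycle 2 Day 22: 16 − 8 = 8 forgone.
- After Cycle 4 Day 15: 16 − 12 = 4 forgone.
- After Cycle 6 Day 15: 16 − 16 = 0 forgone.

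From Cycle 7 one dose per cycle is added in every case. These are upper bounds, because daratumumab might be held for the event anyway and continuation needs agreement.

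**The case against.** The strongest reply is that 3.5 was meant to stop only the causative drug. It speaks of investigational product without the word 'all', whereas Sections 3.1 and 3.5.1 say 'all study treatment' when every drug is to stop. The bullet is tied to nivolumab, and the October 2015 protocol text in the same file has the bullet without that attribution, which fits a nivolumab-directed rule. Section 4.1.5 tells sites to consult the medical monitor on discontinuation questions, so few would act on 3.5 alone.

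This is probably the intent, and it keeps the practical risk low. It does not remove the textual conflict. Pregnancy, progression and withdrawal of consent stand under the same lead-in and make sense only if both antibodies stop. One lead-in cannot mean both drugs for those reasons and one drug for uveitis without saying so.

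A second reply concerns Section 4.1.5.2, and it succeeds. A reader might infer that 4.1.5.2 orders a mere delay of daratumumab for this event. The delay rule is for toxicity related to 'the study drug', which in that section may mean daratumumab alone, so it may not reach uveitis attributed to nivolumab. Nor is the absence of uveitis from the permanent-stop list a contrary instruction. That list also omits pregnancy, progression and withdrawal of consent, each of which ends daratumumab under 3.5.

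**Conclusion.** The point stands as a conflict between instructions. Section 3.5 with the Section 4 definition requires both antibodies to stop for Grade 3-4 nivolumab-related uveitis. Section 4.1.5.1 ends nivolumab, and Sections 3.1, 3.5.1 and 4.1.5 conditionally allow daratumumab to continue.

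The impact is small. It is confined to treatment received and to discontinuation records in nivolumab-treated subjects who have the event. The case counts above rest wholly on the assumed 0.5% to 5% and should not be read as a forecast.

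Two wider inferences are not supported. One is that the trial's results are at risk: no endpoint definition, sample size or error rate depends on this rule, and Section 3.6 keeps subjects who stop before progression in follow-up for PFS. The other is that the neighbouring bullet, "Severe nivolumab immune-mediated adverse events, as described in" Appendix 5, carries the same conflict. That appendix is not in the available text, so no claim is made about the bullet. Section 4.1.5.1 also refers to Appendix 5, which might itself say which drug stops for uveitis. The sponsor can check that directly.

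**What to change.** Reword the one bullet in Section 3.5 so that it names the drug: "Grade 3 or 4 uveitis related to nivolumab": permanently discontinue nivolumab; whether daratumumab continues is decided under the continuation criteria in 3.5.1 and under 4.1.5.2. Because the bullet would then point to 4.1.5.2, it would help to state there whether toxicity attributed to nivolumab triggers the daratumumab delay.

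The cost is a wording change at the next revision and a note to sites. No procedure, data item or analysis changes.
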